13.3 OPEN Registration Requirements

Patient enrollment will be facilitated using the Oncology Patient Enrollment Network (OPEN). OPEN is a web-based registration system available on a 24/7 basis. To access OPEN, the site user must have an active CTEP-IAM account (check at <<https://ctepcore.nci.nih.gov/iam>>) and a 'Registrar' role on either the LPO or participating organization roster. Registrars must hold a minimum of an AP registration type.

All site staff will use OPEN to enroll patients to this study. It is integrated with the CTSU Enterprise System for regulatory and roster data and, upon enrollment, initializes the patient in the Rave database. OPEN can be accessed at <https://open.ctsu.org> or from the OPEN tab on the CTSU members' side of the website at <https://www.ctsu.org>. To assign an IVR or NPIVR as the treating, crediting, consenting, drug shipment (IVR only), or investigator receiving a transfer in OPEN, the IVR or NPIVR must list on their Form FDA 1572 in RCR the IRB number used on the site's IRB approval.

OPEN will also ask additional questions that are not present on the SWOG Registration Worksheet. The individual registering the patient must be prepared to provide answers to the following questions:

- a. Institution CTEP ID
- b. Protocol Number
- c. Registration Step
- d. Treating Investigator
- e. Credit Investigator
- f. Patient Initials
- g. Patient's Date of Birth
- h. Patient SSN (SSN is desired, but optional. Do not enter invalid numbers.)
- i. Country of Residence
- j. ZIP Code
- k. Gender (select one):
 - Female Gender
 - Male Gender
- l. Ethnicity (select one):
 - Hispanic or Latino
 - Not Hispanic or Latino
 - Unknown

- m. Method of Payment (select one):
 - Private Insurance
 - Medicare
 - Medicare and Private Insurance
 - Medicaid
 - Medicaid and Medicare
 - Military or Veterans Sponsored NOS
 - Military Sponsored (Including Champus & Tricare)
 - Veterans Sponsored
 - Self Pay (No Insurance)
 - No Means of Payment (No Insurance)
 - Other
 - Unknown

- n. Race (select all that apply):
 - American Indian or Alaska Native
 - Asian
 - Black or African American
 - Native Hawaiian or other Pacific Islander
 - White
 - Unknown

13.4 Registration Procedures

- a. All site staff (SWOG and CTSU Sites) will use OPEN to enroll patients to this study. OPEN is a web-based application that is integrated with the CTSU Enterprise System for regulatory and roster data and, at the time of patient registration, initializes the patient in the Rave database. OPEN can be accessed at <https://open.ctsu.org> or from the OPEN tab on the CTSU members' side of the website at <https://www.ctsu.org>, or from the OPEN Patient Registration link on the SWOG CRA Workbench.

- b. Prior to accessing OPEN site staff should verify the following:
 - All eligibility criteria have been met within the protocol stated timeframes and the affirmation of eligibility on the Registration Worksheet has been signed by the registering investigator or another investigator designate. Site staff should refer to [Section 5.0](#) to verify eligibility.
 - All patients have signed an appropriate consent form and HIPAA authorization form (if applicable).
 - The study site is listed as "approved" in the CTSU RSS.

- c. Access requirements for OPEN:
 - Site staff will need to be registered with CTEP and have a valid and active CTEP-IAM account. This is the same account (user ID and password) used for the CTSU members' web site. Additional information about obtaining a CTEP-IAM account can be found at http://ctep.cancer.gov/branches/pmb/associate_registration.htm. Questions should be directed to the CTEP Associate Registration Help Desk by e-mail at [contact].
 - To perform registrations, the site user must have been assigned the 'Registrar' role on the SWOG or CTSU roster.

1. If you are a SWOG member, to perform registrations on SWOG protocols you must have an equivalent 'Registrar' role on the SWOG roster. Role assignments are handled through SWOG.
2. If you are not a SWOG member, to perform registrations on SWOG protocols you must have the role of Registrar on the CTSU roster. Site and/or Data Administrators can manage CTSU roster roles via the new Site Roles maintenance feature under RSS on the CTSU members' web site. This will allow them to assign staff the "Registrar" role.

Note: The OPEN system will provide the site with a printable confirmation of registration and treatment information. Please print this confirmation for your records.

- d. Further instructional information is provided on the OPEN tab of the CTSU members' side of the CTSU website at <https://www.ctsu.org> or at <https://open.ctsu.org>. For any additional questions contact the CTSU Help Desk at [name] or [contact].

13.5 After Hours Registration

Patients participating in the non-randomized portion of the study may be registered under SWOG Policy #12. This policy specifies that registrations to the non-randomized portion of a study (1) after regular business hours (e.g., on holidays or weekends), or (2) while the site is unable to access the online registration program, may be completed by calling the Data Operations Center rather than using OPEN. To implement SWOG Policy #12 correctly, the institution must call the Data Operations Center leaving a voice mail message on the day treatment is to begin.

The **S1316** Registration of Non-Randomized Patients during Holidays and Weekends form must be completed prior to making the phone call and is available on the protocol abstract page of the SWOG Website (www.swog.org) and CTSU protocol page (www.ctsu.org).

For the initial registration, call [name] with the following information:

- a. Caller's full name and phone number
- b. Study Number: **S1316**
- c. Treating investigator
- d. Treating institution
- e. Patient Initials
- f. Date of Registration
 - Name/contact number of **S1316** CRA/RN authorized to register patients in OPEN at registering institution

13.6 Exceptions to SWOG registration policies will not be permitted.

- a. Patients must meet all eligibility requirements.
- b. Institutions must be identified as approved for registration.

- c. Registrations may not be cancelled.
- d. Late registrations (after initiation of treatment) will not be accepted.

14.0 DATA SUBMISSION SCHEDULE

14.1 Data Submission Requirement

Data must be submitted according to the protocol requirements for **ALL** patients registered, whether or not assigned treatment is administered, including patients deemed to be ineligible. Patients for whom documentation is inadequate to determine eligibility will generally be deemed ineligible.

14.2 Master Forms

Master forms can be found on the protocol abstract page on the SWOG website (www.swog.org) and (with the exception of the sample consent form and the Registration Worksheet) must be submitted on-line via the Web; see [Section 14.3a](#) for details.

14.3 Data Submission Procedures

- a. Data collection for this study will be done exclusively through the Medidata Rave® clinical data management system. Access to the trial in Rave is granted through the iMedidata application to all persons with the appropriate roles assigned in Regulatory Support System (RSS). To access Rave via iMedidata, you must have an active CTEP-IAM account (check at <https://ctepcore.nci.nih.gov/iam>) and the appropriate Rave role (Rave CRA, Read-Only, CRA Lab Admin, SLA, or Site Investigator) on either the LPO or participating organization roster at the enrolling site. To hold the Rave CRA role or CRA Lab Admin role, the user must hold a minimum of an AP registration type. To hold the Rave Site Investigator role, the individual must be registered as an NPIVR or IVR. Associates can hold read-only roles in Rave. If the study has a DTL, individuals requiring write access to Rave must also be assigned the appropriate Rave tasks on the DTL.

Upon initial site registration approval for the study in RSS, all persons with Rave roles assigned on the appropriate roster will be sent a study invitation e-mail from iMedidata. To accept the invitation, site users must log into the Select Login (<https://login.imedidata.com/selectlogin>) using their CTEP-IAM user name and password, and click on the “accept” link in the upper right-corner of the iMedidata page. Please note, site users will not be able to access the study in Rave until all required Medidata and study specific trainings are completed. Trainings will be in the form of electronic learnings (eLearnings), and can be accessed by clicking on the link in the upper right pane of the iMedidata screen.

Users that have not previously activated their iMedidata/Rave account at the time of initial site registration approval for the study in RSS will also receive a separate invitation from iMedidata to activate their account. Account activation instructions are located on the CTSU website, Rave tab under the Rave resource materials (Medidata Account Activation and Study Invitation Acceptance). Additional information on iMedidata/Rave is available on the CTSU members' website under the Rave tab at www.ctsu.org/RAVE/ or by contacting the CTSU Help Desk at [name] or by e-mail at [contact].

b. Rave® may also be accessed via the SWOG CRA Workbench. Go to the SWOG web site (<http://swog.org>) and logon to the Members Area using the SWOG Roster ID Number and password. After logging on, click on *Workbenches*, then *CRA Workbench* to access the home page for the CRA Workbench and follow the link to Rave® provided in the left-hand navigation panel.

To access the CRA Workbench the following must be done (in order):

1. Registering individual is entered into the SWOG Roster and issued a SWOG Roster ID Number,
2. Registering individual is associated as an investigator or CRA/RN at the institution where the patient is being treated or followed,
3. Sites local Web User Administrator has added registering individual as a web user and has given you the appropriate system permissions to view data for that institution.

For assistance with points 1 and 2 call the Operations Office at [name]. For point 3, contact your local Web User Administrator (refer to the "Who is my Web User Administrator?" function on the swog.org Members logon page).

For difficulties with the CRA Workbench, please e-mail [contact].

c. Institutions participating through the Cancer Trials Support Unit (CTSU) please refer to the [CTSU](#) Participation Table on Page 3.

14.4 Data Submission Overview and Timepoints

a. WITHIN 24 HOURS OF REGISTRATION:

S1316 Dietary Recall Contact Information Form (see Model Consent Form)

b. WITHIN 7 DAYS OF REGISTRATION:

Submit the following:

S1316 Onstudy Form

S1316 Cover Sheet for Patient-Completed Questionnaires

Baseline **S1316** MDASI-GI

Baseline **S1316** EQ-5D-5L

Pathology Report of primary intra-abdominal cancer

Radiology reports from all scans (including CT scans) performed to assess MBO at baseline.

c. WITHIN 14 DAYS AFTER INITIAL HOSPITAL DISCHARGE FOR TREATMENT OF MBO:

Submit the following:

S1316 Malignant Bowel Obstruction Treatment Form

S1316 Malignant Bowel Obstruction Treatment Complications Form

S1316 Somatostatin Analogue Treatment Form

CLOSED EFFECTIVE 5/15/2020

d. WITHIN 7 DAYS OF EACH WEEKLY ASSESSMENT THROUGH WEEK 13:

Submit the following:

S1316 Cover Sheet for Patient-Completed Questionnaires

S1316 MDASI-GI

S1316 EQ-5D-5L (Weeks 2, 4, 8, and 12 only)

S1316 MBO Assessment

e. WITHIN 14 DAYS AFTER WEEK 13:

Submit the following:

S1316 Hospitalization Days Record

NOTE: The data for this form should be extrapolated from the discharge summaries.

f. WITHIN 14 DAYS AFTER EACH HOSPITAL DISCHARGE FOR HOSPITALIZATION FOR ANY REASON THROUGH WEEK 13:

Submit the following:

S1316 Malignant Bowel Obstruction Treatment Form

S1316 Malignant Bowel Obstruction Treatment Complications Form

S1316 Somatostatin Analogue Treatment Form

Source documentation for hospital admission and discharge dates (discharge summary or death summary) and operative reports, if applicable.

g. WITHIN 14 DAYS OF EACH ASSESSMENT EVERY 4 WEEKS AFTER WEEK 13:

Submit the following:

S1316 Cover Sheet for Patient-Completed Questionnaires

S1316 MDASI-GI

S1316 MBO Follow Up Form

h. WITHIN 3 DAYS OF REMOVAL FROM PROTOCOL FOLLOW-UP:

Submit the **S1316** Off Protocol Notice and final **S1316** Follow-Up Form

i. WITHIN 4 WEEKS OF KNOWLEDGE OF DEATH:

Submit the Notice of Death, **S1316** Off Protocol Notice, and final **S1316 Follow-Up Form** (if the patient was still on protocol follow-up)

15.0 SPECIAL INSTRUCTIONS

15.1 Patient Questionnaires: Instructions for Administration

- a. It is important to note that the time frame for providing ratings for the S1316 MDASI-GI should be rated with respect to the past 7 days. The schedule for the assessments is:
 1. **S1316** MDASI-GI – Baseline, each week from Week 1-13, and every 4 weeks until Week 53.
 2. **S1316** EQ-5D-5L – Baseline, Weeks 2, 4, 8, and 12.
- b. Administration of Questionnaires
 1. The first time the patient completes the questionnaires: Please read to the patient the instructions attached to each patient questionnaire. Explain the specific administration times for this protocol. Patients should be directed to report all symptoms and limitations whether or not they are related to the cancer, MBO, or its treatment.
 2. It is permissible to assist patients with completing the questionnaires being careful not to influence the patient's response. Note on the **S1316** Cover Sheet for Patient-Completed Questionnaires what assistance was required and indicate reason (e.g., elderly, too sick, etc.). Discourage family members from: 1) being present while the patient completes the questionnaire and/or 2) influencing patient responses to the questions.
 3. It is very important to review the questionnaires after the patient has completed them to be sure all of the questions have been answered and that only one answer is marked. a) If the patient has marked more than one answer per question, ask the patient which answer reflects how she is feeling. b) If the patient has skipped a question, tell the patient that a question was not answered and ask if she would like to answer the question. Always give the patient the option to refuse. Indicate on the form by the question that the patient did not want to answer this question.
 4. If a patient refuses or cannot complete the questionnaire for some reason, then this must be documented on the **S1316** Cover Sheet for Patient Completed Questionnaires and submitted to the Data Operations Center in Seattle (see [Section 14.3](#)).
 5. If a patient misses an assessment, a telephone interview must be scheduled and completed within two days of the originally scheduled time.

c. Additional quality control procedures:

1. When a patient is registered on **S1316**, a calendar should be made with dates of upcoming patient-completed questionnaires noted. A copy of this calendar can be given to the patient with the notation that the questionnaires should be completed. You may wish to photocopy the Study Calendar, [Section 9.0](#), and include the patient's name and specific dates. A copy of this should be kept in the patient file.
2. If a patient refuses or cannot complete the patient questionnaires at one time point, he or she should be asked to do so at the next scheduled assessment time. Submit the **S1316** Cover Sheet for Patient-Completed Questionnaires documenting the reason why the questionnaires were not done.
3. Anyone involved in the collection of quality of life data in SWOG trials should review the training program available on the SWOG website accessible from three locations. On the SWOG Home Page (prior to member login), in the **QUICKLINKS** section on the bottom right corner of the page, there is a link to the Patient Reported Outcomes Training. The other two locations that the training is available are after SWOG member login on the CRA Workbench. The Training section and the New CRAs! section both contain access to the Patient Reported Outcomes (PROs) training module. The training program is a narrated set of slides designed to standardize the way quality of life data is collected from patients. Questions regarding the quality of life assessments can be addressed to the SWOG Data Operations Office ([name]).

d. **S1316** Cover Sheet for Patient-Completed Questionnaires

For each time point, the nurse or CRA completes the **S1316** Cover Sheet for Patient-Completed Questionnaires. The Cover Sheet is submitted with the set of patient-completed forms at each scheduled assessment. The Cover Sheet is very important for tracking how and when the patient forms were completed. When a patient-completed form is not administered at a scheduled time point, it is important to know why the assessment did not occur; the form includes potential reasons for a patient not completing a form. See [Section 14.0](#) for data submission guidelines.

16.0 ETHICAL AND REGULATORY CONSIDERATIONS

The following must be observed to comply with Food and Drug Administration regulations for the conduct and monitoring of clinical investigations; they also represent sound research practice:

Informed Consent

The principles of informed consent are described by Federal Regulatory Guidelines (Federal Register Vol. 46, No. 17, January 27, 1981, part 50) and the Office for Protection from Research Risks Reports: Protection of Human Subjects (Code of Federal Regulations 45 CFR 46). They must be followed to comply with FDA regulations for the conduct and monitoring of clinical investigations.

Institutional Review

This study must be approved by an appropriate institutional review committee as defined by Federal Regulatory Guidelines (Ref. Federal Register Vol. 46, No. 17, January 27, 1981, part 56) and the Office for Protection from Research Risks Reports: Protection of Human Subjects (Code of Federal Regulations 45 CFR 46).

Monitoring

This study will be monitored by the Clinical Data Update System (CDUS) Version 3.0. Cumulative CDUS data will be submitted quarterly to CTEP by electronic means. Reports are due January 31, April 30, July 31 and October 31.

Confidentiality

Please note that the information contained in this protocol is considered confidential and should not be used or shared beyond the purposes of completing protocol requirements until or unless additional permission is obtained.

16.1 Adverse Event Reporting Requirements

a. Purpose

Adverse event data collection and reporting, which are required as part of every clinical trial, are done to ensure the safety of patients enrolled in the studies as well as those who will enroll in future studies using similar agents. Adverse events are reported in a routine manner at scheduled times during a trial. (Directions for routine reporting are provided in [Section 14.0](#).) Additionally, certain adverse events must be reported in an expedited manner to allow for more timely monitoring of patient safety and care. The following guidelines prescribe expedited adverse event reporting for this protocol. See also [Appendix 18.1](#) for general and background information about expedited reporting.

b. Reporting method

This study requires that expedited adverse events be reported using the Cancer Therapy Evaluation Program Adverse Event Reporting System (CTEP-AERS). CTEP's guidelines for CTEP-AERS can be found at <http://ctep.cancer.gov>. A CTEP-AERS report must be submitted to the SWOG Operations Office electronically via the CTEP-AERS Web-based application located at http://ctep.cancer.gov/protocolDevelopment/electronic_applications/adverse_events.htm.

In the rare event when internet connectivity is disrupted an electronic report MUST be submitted immediately upon re-establishment of internet connection.

c. When to report an event in an expedited manner

When the adverse event requires expedited reporting, submit the report within 10 calendar days of learning of the event.

d. Other recipients of adverse event reports

The SWOG Operations Office will forward reports and documentation to the appropriate regulatory agencies and drug companies as required.

Adverse events determined to be reportable to the Institutional Review Board responsible for oversight of the patient must be reported according to local policy and procedures.

e. Expedited reporting for commercial agents

Commercial reporting requirements are provided in [Table 16.1](#). If there is any question about the reportability of an adverse event or if on-line CTEP-AERS cannot be used, please telephone or email the SAE Program at the Operations Office, [name] or [contact], before preparing the report.

Table 16.1. Expedited reporting requirements for adverse events experienced by patients within 30 days of the last administration of the commercial agents and/or surgery.

ATTRIBUTION	Grade 4		Grade 5 ^a	
	Unexpected	Expected	Unexpected	Expected
Unrelated or Unlikely			CTEP-AERS	CTEP-AERS
Possible, Probable, Definite	CTEP-AERS		CTEP-AERS	CTEP-AERS
CTEP-AERS: Indicates an expedited report is to be submitted via CTEP-AERS within 10 calendar days of learning of the event ^b .				
^a This includes all deaths within 30 days of the last dose of treatment with a commercial agent(s) or within 30 days of the surgical procedure regardless of attribution. Any death that occurs more than 30 days after the last dose of treatment with a commercial agent(s) or within 30 days of the surgical procedure, and is attributed (possibly, probably, or definitely) to the agent(s) or surgery and is not due to cancer recurrence must be reported according to the instructions above.				
^b Submission of the on-line CTEP-AERS report plus any necessary amendments generally completes the reporting requirements. You may, however, be asked to submit supporting clinical data to the Operations Office in order to complete the evaluation of the event. If requested, the specified data should be sent within 5 calendar days by fax to [contact].				

f. **Reporting Pregnancy, Fetal Death, and Death Neonatal**

1. **Pregnancy** Study participants who become pregnant while on study; that pregnancy should be reported in an expedited manner via CTEP-AERS as **Grade 3 “Pregnancy, puerperium and perinatal conditions – Other (pregnancy)”** under the **Pregnancy, puerperium and perinatal conditions** SOC.

Additionally, the pregnancy outcome for patients on study should be reported via CTEP-AERS at the time the outcome becomes known, accompanied by the same Pregnancy Report Form used for the initial report.

Fetal Death Fetal Death defined in CTCAE as “A disorder characterized by death in utero; failure of the product of conception to show evidence of respiration, heartbeat, or definite movement of a voluntary muscle after expulsion from the uterus, without possibility of resuscitation” should be reported expeditiously as **Grade 4 “pregnancy, puerperium and perinatal conditions – Other (pregnancy loss)”** under the **Pregnancy, puerperium and perinatal conditions** SOC.

2. **Death Neonatal** Neonatal death, defined in CTCAE as “A disorder characterized by cessation of life occurring during the first 28 days of life” that is felt by the investigator to be at least possibly due to the investigational agent/intervention should be reported expeditiously.

A neonatal death should be reported expeditiously as **Grade 4 “General disorders and administration – Other (neonatal loss)”** under the **General disorders and administration** SOC.

*Fetal death and neonatal death should **NOT** be reported as a Grade 5 event. If reported as such, the CTEP-AERS interprets this as a death of the patient being treated.*

NOTE: When submitting CTEP-AERS reports for “Pregnancy, “Pregnancy loss”, or “Neonatal loss”, the Pregnancy Information Form should also be completed and faxed with any additional medical information to [contact]. The potential risk of exposure of the fetus to the investigational agent(s) or chemotherapy agent(s) should be documented in the “Description of Event” section of the CTEP-AERS report.

The Pregnancy Information Form is available at:
http://ctep.cancer.gov/protocolDevelopment/adverse_effects/htm

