3.0 DRUG INFORMATION

Drug information is not applicable to this study.

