5.1 Disease Related Criteria

- a. Patient must have malignant bowel obstruction (MBO) as evidenced by all of the following (24):
 - Clinical evidence of a small bowel obstruction (via history, physical, and radiographic examination)
 - Bowel obstruction below (distal to) ligament of Treitz
 - Intra-abdominal primary cancer with incurable disease

- b. Patients must have malignant bowel obstruction due to an intra-abdominal primary cancer, (i.e. GI, pancreas, ovarian, uterine, cervical, kidney, bladder, prostate, GIST [all sites], and sarcoma). Patients may still have primary tumor as long as it is not a primary large bowel obstruction from colorectal cancer.
- c. Patient must be able to tolerate a major surgical procedure based on clinical evaluation, status of their cancer, and any other underlying medical problems.
- d. A member of the patient's surgical team must indicate equipoise for the benefit of the surgical treatment for MBO. The surgeon must respond "Yes" to each of the following questions and sign the **S1316** Surgical Equipoise Documentation form for the patient to be eligible:
 1. Is surgery for treatment of malignant bowel obstruction (MBO) being considered for this patient?
 2. Do you have equipoise? If the treating team finds that an operation is required (e.g., for acute abdomen), or they would not offer the patient an operation (e.g., patient is too weak to tolerate surgery), then there is no equipoise.
- e. Patients must not have signs of bowel perforation necessitating surgery or "acute" abdomen evidenced by peritonitis on physical exam within 2 days prior to registration.

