5.2 Clinical/Laboratory Criteria

- a. Patients must be registered to the study within 3 working days after being seen by surgical team for MBO or within 3 working days after completion of indicated treatment (e.g. TPN, anticoagulation reversal) to make them eligible for surgical intervention, whichever is later, and prior to any treatment (surgical or non-surgical) for MBO. Treatment is defined as any medication or invasive interventions beyond nasogastric decompression, hydration, pain medications or antiemetic medications. NOTE: Somatostatin analogues may be used prior to registration if that use is limited to not more than the two days just prior to registration.
- b. Radiographic confirmation of MBO is required prior to registration. Scans may have been done before or after admission; scans done prior to admission must have been completed within 14 days prior to admission. CT scans are preferred.
- c. Patients must have Zubrod Performance Status of 0-2 within 7 days prior to hospitalization (see [Section 10.4](#)).
- d. Serum albumin must be planned to be collected after admission, but prior to treatment.
- e. Patients must be able to complete the study questionnaires in English or Spanish.
- f. Patients must be ≥ 18 years of age.
- g. Prestudy history and physical must be obtained within 3 days prior to registration.

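### Table 16.1, footnote a: the surgery limb of the second sentence repeats the early 30-day window, so one kind of late surgery-attributed death needs no 10-day report (minor)

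*Combined protocol and SAP*

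**What the plan says.** Section 16.1c sets a limit of 10 calendar days, from learning of the event, for any adverse event that needs an expedited report. Table 16.1 lists which events those are. Its title restricts it to events "experienced by patients within 30 days of the last administration of the commercial agents and/or surgery". Within that scope all four Grade 5 cells call for a CTEP-AERS report.

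Footnote a to the Grade 5 column has two sentences.

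- Sentence 1 brings in every death up to 30 days after the last agent dose, or "within 30 days of the surgical procedure regardless of attribution".
- Sentence 2 addresses deaths with this timing: "more than 30 days after the last dose of treatment with a commercial agent(s) or within 30 days of the surgical procedure, and is attributed" to treatment. Its full condition is that the death is "attributed (possibly, probably, or definitely) to the agent(s) or surgery and is not due to cancer recurrence must be reported".

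Section 14.4i separately asks for a Notice of Death within 4 weeks of knowledge of the death. Follow-up runs to 53 weeks (Section 7.8), so deaths well beyond 30 days after an operation fall inside it.

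**The concern.** Sentence 2 reads as the extension of sentence 1 to later deaths, on condition that they are attributed to treatment and not due to recurrence. It names surgery as one of the two possible attributions. For the agent it moves to the later window. For surgery it stays in the window that sentence 1 has already dealt with. The surgery limb then does no work, and nothing else in the sentence picks up a late death attributed to the operation alone.

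This is an operative safety-reporting rule, and surgery is one of the two treatments being compared. A site that applied the text literally would expedite a late death it attributed to a drug, but not the equivalent death it attributed to the operation in a patient who had no such drug.

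**Working it through.** The plan gives no figure to reproduce here. The check is to apply the footnote, as printed, to each possible history, and then again with the surgery limb of sentence 2 read as more than 30 days.

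**Rules applied**

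- Sentence 1: report if the last agent dose or the surgery was 30 days or less before death.
- Sentence 2 as printed: report if (last agent dose more than 30 days before death, or surgery 30 days or less before death), and the death is attributed to agent or surgery, and it is not due to recurrence.
- Sentence 2 in parallel form: the same, with surgery more than 30 days before death.
- A patient who never had a commercial agent has no last dose, so neither agent limb applies.

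**Deaths attributed to surgery, not due to recurrence**

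| Surgery before death | Commercial agent | As printed | Parallel form |
|---|---|---|---|
| 30 days or less | any history | report (sentence 1) | report (sentence 1) |
| more than 30 days | last dose 30 days or less before death | report (sentence 1) | report (sentence 1) |
| more than 30 days | last dose more than 30 days before death | report (sentence 2, agent limb) | report (sentence 2, either limb) |
| more than 30 days | none given | **no report** | **report (sentence 2, surgery limb)** |

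**All other deaths**

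- Attributed to an agent, not due to recurrence: the patient had an agent, so sentence 1 or the agent limb applies. There is no difference between the two forms.
- Attributed to neither treatment, or due to recurrence: sentence 2 cannot apply in either form, so sentence 1 alone decides. No difference.

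The two forms therefore differ in exactly one case, the last row of the table. The surgery limb as printed adds no death to sentence 1, because it requires surgery 30 days or less before death and sentence 1 reports all of those.

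**Whether another provision closes the gap**

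- The table title has the same 30-day limit, so sentence 2 is the only expedited route for later deaths.
- Section 16.1e offers a contact "If there is any question about the reportability of an adverse event or if on-line CTEP-AERS cannot be used". It is a way to ask, not a requirement to report.
- Section 16.1d leaves IRB reporting to local policy.
- Section 16.1a points to Appendix 18.1 for background on expedited reporting, but that appendix is the dietary recall script.
- The Notice of Death does capture the death, but it is not a CTEP-AERS report. Both clocks start at knowledge of the death, so the deadlines lie 4 × 7 − 10 = 28 − 10 = 18 days apart.

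**Whether the case can arise**

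Section 7.2 names no drug for the surgery arms. Section 7.3 makes the somatostatin analogue optional, and does so for the non-surgical arms. Section 3.0 says only that "Drug information is not applicable to this study", and no section defines commercial agent.

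**The case against.** The best case against the point is that this is a slip with little consequence, and most of that stands.

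A reader might infer that the footnote contradicts itself, because sentence 2 attaches conditions to early surgical deaths that sentence 1 reports unconditionally. The text does not support that. Sentence 2 says certain deaths must be reported. It does not say only those, so it withdraws nothing from sentence 1, and a site can obey both. The defect is a redundant phrase and a resulting omission.

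A reader might also use Section 5.2a to decide which drugs count as commercial agents, since it says "Treatment is defined as any medication or invasive interventions beyond nasogastric decompression, hydration, pain medications or antiemetic medications". That definition serves eligibility before registration and does not mention commercial agents. If the term covers any marketed drug given in routine care, almost no operated patient would be without one and the gap may be empty. If it covers only drugs given to treat the obstruction, the gap may contain some patients. The documents do not settle which.

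It is fair, too, that an awkward footnote may prompt a site to use the Section 16.1e contact, and that Section 16.1b refers to external CTEP guidelines that are not reproduced here. What a site would actually do is therefore not shown. But a site that finds the printed words clear has no question to raise, and nothing in these documents supplies the missing requirement.

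Finally, the intended rule is inferred. The reference to agent or surgery in sentence 2 makes the later window the likely intention, but the sponsor has to confirm it.

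**Conclusion.** The point holds as a minor error in the wording. The surgery limb of sentence 2 is redundant, and one case is left without a 10-day report: no commercial agent, death more than 30 days after surgery, attributed to surgery, not due to recurrence.

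This should not be read as a general failure to report late surgical deaths. Operated patients who also had a commercial agent are covered by sentence 1 or by the agent limb. Deaths due to recurrence that fall outside both 30-day windows are exempt under either wording. That exemption matters in a population whose entry criterion is "Intra-abdominal primary cancer with incurable disease".

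The number of patients affected is unknown and may be zero. The primary endpoint, sample size and power do not depend on the footnote. No monitoring decision is shown to depend on it either: Section 11.7 plans no formal interim safety analysis, and the monitoring committee receives reports every 6 months. The conclusion assumes that the footnote is applied as printed and that the external guidelines do not supply the missing rule.

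**What to change.** The sponsor should reconcile the two sentences of footnote a. The most likely correction is to make the surgery limb of sentence 2 refer, like the agent limb, to deaths more than 30 days afterwards, and to leave the attribution and recurrence conditions as they are.

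The cost is a one-phrase amendment and at most a few more expedited reports, possibly none. The document is stamped closed effective 5/15/2020. If that means closed to accrual, the new wording would act only on remaining follow-up: 53 × 7 = 371 days, so to about 21 May 2021 for a patient registered on the closing date.
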